4.0 SUBJECT REGISTRATION

The subjects will be recruited by the PI, co-investigators, or authorized study staff at the orthopaedic surgery clinic or prior to their ACDF surgery in the pre-operative hold area in. The study will be reviewed with the subjects and they will be consented by the PI, co-investigator, or other authorized study staff.

Each collaborating site will be involved in subject recruitment, consent, and all data collection for any patients that are enrolled in the study at each respective site.

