5.0 STUDY DESIGN & METHODS

We intend to prospectively evaluate 85 patients as part of a single blind, randomized controlled study. Subjects would be randomized to group I (control group, no steroid), group II (10 mg of intraoperative intravenous decadron with gel foam sponge placed on cervical plate), or group III (40mg of triamcinolone on gel foam sponge dabbed on the anterior cervical plate). Subjects will be blinded to the treatment arm. Randomization will take place on the day of surgery. 85 envelopes will be sealed, 25 of which will contain a document specifying “control”, “iv steroids”, or “steroid sponge”. The 75 envelopes will then be shuffled to create a random assortment. The circulating nurse in the OR will at random choose one envelop prior to the start of the operative procedure. This will in turn specify the treatment group for each patient.

There is no standard of care regarding the use of IV or local steroids in the setting of ACDF. Currently, the use of either IV or local steroids is at the discretion of the attending surgeon. To my knowledge, there are several spine surgeons at our institution that currently use no steroid, and others who use a combination of IV and/or local steroids.

The primary outcome measure is the incidence of dysphagia as measured by Eating Assessment Tool (EAT-10) and the Bazaz score. The patients will prospectively fill out these surveys preoperatively, post-operative day 1, week 2, week 6, month 3, month 6, and 1 year as a measure of dysphagia. The standard of care is to see patients in the office at 2 weeks, 6 weeks, 3 months, 6 months, and 1 year after surgery, and therefore, no extra visits will be necessary for this study. X-rays will be taken at 6 weeks, 3

months, and 12 months post-op, which is the current standard of care. No additional x-rays will be obtained.

A secondary outcome measure will be the incidence of dysphonia, as measured by the Voice Handicap Index (VHI-10), as well as other validated outcome measures (NDI, VAS, EQ-5D). The questionnaires will take approximately 20 minutes to complete and will be administered in the hospital, during the post-operative clinic visits with the surgeon, or over the phone. The surgeons will also listen to the patient's voice at these different time points and comment on dysphonia as being absent, mild, moderate, or severe.

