Additionally, a chart review will be performed from 1/1/2013 to 12/30/2016 from NMH Medical records (PRIMES, Cerner PowerChart) and NMFF Medical Records (EpicCare, IDX/GE Centricity) to obtain the following data: Complications such as infection, post-operative hematoma, airway compromise, and recurrent laryngeal nerve palsy. All data collected from chart review will be de-identified and noted on the Data Collection Form. Each subject will be assigned a study number and all data will be linked to that number using the Coded Identifier List. The PI will identify which charts will be reviewed. The chart review will be performed by the PI, co-investigators, or authorized study coordinator.

There are potential physical risks from being in this study. The use of steroids may have an adverse effect on wound healing and/or transiently elevate blood sugar. There have been no documented wound complications from using either IV or local steroids in the setting of ACDF. Furthermore, we purposely excluded patients with a history of diabetes or other endocrine disorder in an attempt to minimize this potential side-effect or complication. Another possible risk related with participation in this study is the loss of privacy. To reduce these risks, all of the information collected will be de-identified and stored in a password protected file on a password protected computer. Additionally, some of the questions asked in the surveys may be upsetting, or the subject may feel uncomfortable answering them. If the subject does not wish to answer a question, they may skip it and go to the next question.

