6.0 STATISTICAL PLAN

We will use T score or ANOVA to compare EAT-10 scores, VHI scores, and EQ-5D, and Chi square for subjective findings. The P value will be set at 0.05.

A power analysis was performed to determine the sample size needed. Based on previous studies evaluating the EAT-10 in normal patients and those with dysphasia the analysis concluded: with total sample size 85 (Group I: 25, Group II: 25, Group III: 25) and estimated standard deviation of EAT-10 as 12.7, **power = 0.92**

Drs. [name], [name], and [name], perform approximately 6 ACDFs a month. This would allow us to collect our proposed sample size in approximately 12-14 months.

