7.0 DATA COLLECTION & RECORD KEEPING

All information regarding the nature of the proposed investigation provided to the investigator (with the exception of information required by law or regulations to be disclosed to the IRB, the subject, or the appropriate regulatory authority) will be kept in confidence by the investigator. All personal information will be treated as strictly confidential and not made publicly available. All records and appendices are stored in separate locked filing cabinets as well as a password protected computers which are accessed only by the Principal Investigator, co-investigator, and authorized study staff. All identifiable data will be destroyed a year after the study is complete.

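### The complication chart review stops on a calendar date, 12/30/2016, not at a set time after each surgery, so chart coverage may fall short of a year and the form would not show it

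*Combined protocol and SAP*

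**What the plan says.** Section 5.0 (Study Design & Methods) sets the period and the sources: "a chart review will be performed from 1/1/2013 to 12/30/2016 from NMH Medical records", with NMFF record systems named alongside. The items sought are infection, hematoma, airway compromise and recurrent laryngeal nerve palsy. No time limit counted from surgery is given for any of them. On recording, the section says "All data collected from chart review will be de-identified and noted on the Data Collection Form". That form, in the appendices, has one numbered row per subject (1 to 75) and four complication columns. It has no column for the date or length of review.

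The same section names a risk that the review would help to assess: "The use of steroids may have an adverse effect on wound healing".

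The surrounding timetable is as follows. The Synopsis dates the protocol 12/14/2015 and lists University of Wisconsin-Madison and OrthoCarolina Research Institute among the centers. Section 5.0 looks forward ("We intend to prospectively evaluate 85 patients as part of a single blind, randomized controlled study") and places office visits at "2 weeks, 6 weeks, 3 months, 6 months, and 1 year after surgery". Section 6.0 expects accrual in 12 to 14 months because the named surgeons "perform approximately 6 ACDFs a month". Section 4.0 covers site duties: "Each collaborating site will be involved in subject recruitment, consent, and all data collection for any patients" enrolled there. Section 7.0 adds: "All identifiable data will be destroyed a year after the study is complete".

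**The concern.** Whether the two dates bound the records examined or the period in which staff do the examining, nothing after 12/30/2016 is captured. A patient treated early could have years of chart coverage, and one treated late only weeks. On the form, a blank complication cell after three weeks looks the same as one after a full year. The length of follow-up could be rebuilt from the medical record numbers on the Coded Identifier Form, but only until the identifiers are destroyed.

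What is at stake is the absolute complication rate. If some charts are cut short and this is not recorded, the rates may be too low, in the one dataset that bears on the wound-healing risk the protocol itself raises.

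There is also a smaller textual gap. Section 5.0 names only NMH and NMFF records, while section 4.0 gives every site the data collection for its own patients. No record source or review period is written for the two outside sites. NMH is not spelled out; I read it as a Northwestern hospital.

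**Working it through.** **Inputs.** Window end 12/30/2016 and window start 1/1/2013 (section 5.0); 6 surgeries a month (section 6.0); protocol date 12/14/2015 (Synopsis). The sample size is taken as 75 and as 85, because the plan gives both. The 12-month horizon is borrowed from the visit schedule, since the plan sets none for complications. Enrolment start is not stated and is varied.

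**The plan's own accrual figure.** 75/6 = 12.5 months and 85/6 = 14.2 months, which agrees with the stated 12 to 14.

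**Last surgery date with a full year covered.** 12/30/2016 minus 365 days = 12/31/2015. This needs no accrual assumption. The window closes 382 days after the protocol date.

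**Number short of a horizon of H days.** With even accrual, one surgery falls every 30.44/6 = 5.073 days. Let D be the days from the enrolment start to 12/30/2016, and count each surgery at the end of its interval. The number fully covered is (D − H)/5.073, rounded down; the rest of the 75 or 85 are short.

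For H = 365:

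| Assumed start | D | (D − 365)/5.073 | Short, N = 75 | Short, N = 85 |
|---|---|---|---|---|
| 1/1/2015 | 729 | 71.8 → 71 | 4 (5%) | 14 (16%) |
| 7/1/2015 | 548 | 36.1 → 36 | 39 (52%) | 49 (58%) |
| 12/14/2015 | 382 | 3.4 → 3 | 72 (96%) | 82 (96%) |

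**Latest start with nobody short.** 12/31/2015 minus the accrual period: 75 × 5.073 = 380.5 days gives about 12/16/2014; 85 × 5.073 = 431.2 days gives about 10/26/2014.

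**Shorter horizons.**

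| Assumed start | 6 months (183 d) | 3 months (91 d) | 6 weeks (42 d) |
|---|---|---|---|
| 7/1/2015 | 4 of 75; 14 of 85 | 0; 0 | 0; 0 |
| 12/14/2015 | 36 of 75; 46 of 85 | 18 of 75; 28 of 85 | 8 of 75; 18 of 85 |

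At 6 weeks nobody is short for any start by about 11/4/2015 (N = 75) or 9/14/2015 (N = 85). With a protocol-date start, 382/5.073 = 75.3, so 75 surgeries fall inside the window; with N = 85 the other 10 fall after it closes. Placing surgeries at the middle or start of each interval changes any count by at most one.

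**The case against.** The best counter-argument is that truncation is not shown. The window opens on 1/1/2013 and runs 1,459 days (47.9 months). Accrual plus a year of follow-up needs only 24.5 to 26.2 months, so there is room for everyone if enrolment began by late 2014. A records window opening in 2013 is also hard to square with a first patient in December 2015, so 12/14/2015 may be only a version date. This stands. A reader might infer from the last row of the first table that nearly every patient loses a year's coverage; the documents do not support that, because the start date is not given.

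Several other points also stand:

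- The one-year horizon belongs to the questionnaires and visits. If the complications of interest arise in the first weeks, little is lost unless surgery falls close to or after the end date.
- The rate of 6 a month refers to particular surgeons whose names are removed, so it may not cover all sites. Faster accrual would shrink the loss; ineligibility or refusal would enlarge it.
- A reader might infer that complications at the two outside sites go uncollected. Section 4.0 points the other way, and the form's 75 rows match three arms of 25, not a Northwestern subset. What remains is a need to reconcile the two sections.
- A reader might infer a biased comparison of arms. A calendar cut-off applies alike to concurrently randomised patients, so no arm should be favoured.
- Complications are neither the primary nor a named secondary outcome, and section 6.0 does not mention them. Nerve palsy has partial back-up in the surgeons' voice grading and the VHI-10. Even with full coverage, zero events in 25 patients has an exact 95% upper limit of 1 − 0.025^(1/25) = 13.7%, so per-arm rates will be imprecise in any case.

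None of this removes the rule itself. The plan cannot show that coverage is complete, and its form would not reveal where it is not.

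**Conclusion.** The point holds as a minor safety-reporting issue. It is certain that the review ends on a calendar date, that surgery after 12/31/2015 cannot have a full year of chart coverage, and that the form does not record length of review. The number of patients affected is uncertain: it runs from none to the protocol-date extreme, according to the enrolment start, and rests on even accrual at 6 a month and a borrowed 12-month horizon. The possible consequence is that absolute complication rates are understated. The between-arm dysphagia comparison is not affected. For the two outside sites the documents support only a request to reconcile sections 4.0 and 5.0; patient numbers there are not given, so no loss can be calculated.

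**What to change.** 1. In section 5.0, replace the calendar end date with a fixed window from surgery for every randomised patient, for example to the existing 1-year visit.
2. State that each enrolling site reviews its own records for that window, which reconciles section 5.0 with section 4.0.
3. Add one field to the Data Collection Form: days from surgery to the last record reviewed. A day count, unlike a date, is in keeping with the de-identification statement.
4. In section 6.0, say that every observed complication is counted among all randomised patients, by arm, with the extent of follow-up reported. Event counts with days reviewed would do, as would a person-time or time-to-event estimate. Do not restrict rates to completely reviewed charts: that would drop a patient who had an event and then lacked later records, and could itself lower the rate.

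The cost is a wording amendment through the IRB, one extra field, and chart checks that finish up to 1 year after the last surgery. No visit or procedure is added, and section 4.0 already has each site collecting data on its own patients.

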6.0 STATISTICAL PLAN

We will use T score or ANOVA to compare EAT-10 scores, VHI scores, and EQ-5D, and Chi square for subjective findings. The P value will be set at 0.05.

A power analysis was performed to determine the sample size needed. Based on previous studies evaluating the EAT-10 in normal patients and those with dysphasia the analysis concluded: with total sample size 85 (Group I: 25, Group II: 25, Group III: 25) and estimated standard deviation of EAT-10 as 12.7, **power = 0.92**

Drs. [name], [name], and [name], perform approximately 6 ACDFs a month. This would allow us to collect our proposed sample size in approximately 12-14 months.

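### Section 6.0 gives only a t-test or ANOVA for scores taken at six post-operative times; anyone with no questionnaire at a visit drops out of that test, which attenuates a real later effect if recovered patients respond less

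*Combined protocol and SAP*

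**What the plan says.** Section 5.0 schedules the dysphagia questionnaires "preoperatively, post-operative day 1, week 2, week 6, month 3, month 6, and 1 year", which is one pre-operative and six post-operative assessments. It defines the main outcome as follows: "The primary outcome measure is the incidence of dysphagia as measured by Eating Assessment Tool (EAT-10) and the Bazaz score". No cut-off and no time point are attached to it. Questionnaires may be "administered in the hospital, during the post-operative clinic visits with the surgeon, or over the phone". No call is required after a missed visit, and the plan adds no visits beyond routine follow-up. In the appendix, the identifier form has a telephone column for subjects 39 to 75 but not for subjects 1 to 38. The risk paragraph of section 5.0 adds: "If the subject does not wish to answer a question, they may skip it and go to the next question". No scoring rule for skipped items follows.

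Section 6.0 gives the whole analysis: "We will use T score or ANOVA to compare EAT-10 scores, VHI scores, and EQ-5D, and Chi square for subjective findings". The significance level is the only other rule: "The P value will be set at 0.05". No repeated-measures model, use of the pre-operative score, visit of main interest, analysis set, dropout allowance or missing-data method appears anywhere.

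**The concern.** A t-test or one-way ANOVA at a given visit can use only patients who have a score at that visit. A patient who returned the day-1, week-2 and week-6 questionnaires but nothing at month 6 adds nothing to the month-6 comparison, although the earlier scores show how that patient was recovering. Leaving such patients out is harmless only if absence is unrelated to the scores.

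Five of the six post-operative assessments coincide with routine office visits, and patients who feel well are plausible non-responders. Section 2.0 hypothesises that local steroid reduces dysphagia. If it does, more patients in that arm are well, more are absent, and those left are the worse ones. The trial would then understate the effect it was built to detect.

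Skipped items raise a smaller version of the problem. The total is either missing for someone who did respond, or too low if the answered items are simply added up.

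**Working it through.** **The plan's own figure.** Section 6.0 states power 0.92 "with total sample size 85 (Group I: 25, Group II: 25, Group III: 25) and estimated standard deviation of EAT-10 as 12.7". It gives no EAT-10 difference, so the power cannot be reproduced. It can only be solved backwards, with n = 25 per group and two-sided alpha 0.05:

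Δ = (z₀.₉₇₅ + z₀.₉₂) × SD × √(2/n) = (1.960 + 1.405) × 12.7 × √(2/25) = 12.1 (12.3 with the t distribution).

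At Δ = 12.3, loss that is unrelated to outcome lowers power from 0.92 to 0.89 (10% lost), 0.85 (20%) or 0.80 (30%). The calculation states no allowance for loss.

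**Inputs to the bias illustration.**

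- From section 6.0: 25 per arm, SD 12.7.
- Assumed: normal scores; two arms and two visits; correlation ρ = 0.6 between visits; true early difference 12.7 (1 SD); true later difference 0.6 × 12.7 = 7.62; about 25% of later scores missing overall.
- Assumed mechanism, the same in both arms: the log-odds of being missing rise by g for each SD that the earlier score is lower.

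**Why the estimate shifts.** Among responders in an arm, the mean later score is the true mean plus ρ times the amount by which responders' earlier scores exceed that arm's earlier mean. The observed difference is therefore

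observed = true − ρ × (excess in effective arm − excess in control).

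If the arms have the same score distribution and the same mechanism, the two excesses are equal and the bias is zero.

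**Results (simulated trials; differences in EAT-10 points, true value 7.62).**

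| Mechanism | Responders only | Using the earlier score |
|---|---|---|
| Unrelated to scores | unbiased, SE 4.17 | unbiased, SE 3.98 |
| Earlier score, g = 1 (about 17% v 32% missing) | 6.68 | 7.6 |
| Earlier score, g = 2 | 5.67 | 7.6 |
| Current, unseen score, g = 1 | 6.63 | 6.96 |

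- g = 1: loss (7.62 − 6.68)/7.62 = 12%. The implied gap between the two excesses is 0.94/0.6 = 1.57 points, and 7.62 − 0.6 × 1.57 = 6.68 as above.
- g = 2: loss (7.62 − 5.67)/7.62 = 26%. The estimate moves between about 5.4 and 5.7 according to how the overall missing rate is set.
- Half the missed scores captured by phone: 7.34 at g = 1, a loss of 0.28/7.62 = 4%; 6.93 at g = 2, a loss of 0.69/7.62 = 9%. Full capture removes the bias.
- Absence driven by the current score: the model recovers (6.96 − 6.63)/(7.62 − 6.63) = 0.33/0.99, one third of the loss.
- Absence unrelated to scores: the model still gains a little, 1 − 3.98/4.17 = 5% in standard error.

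**The case against.** **Phone collection.** A reader might infer that anyone who stops attending leaves every later comparison. Section 5.0 does not support that, because a questionnaire may be completed by phone. Only patients with no questionnaire by any route are lost. But permission is not a procedure: nothing triggers a call, and half the identifier form has no place for a number. The risk is reduced, not removed.

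**The method is inferred.** A reader might infer that the plan has chosen a visit-by-visit analysis of attenders. It has not said so: no visit is named, and ANOVA could mean a repeated-measures form. That is fair, and the fault is partly one of omission. It does not rescue the plan. A plain test at even one chosen visit omits patients without a score there, and classical repeated-measures ANOVA omits anyone with a single gap.

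**Bias is not automatic.** A reader might infer that recovery-driven absence always distorts the comparison, or could create a false effect. Under a mechanism shared by all arms, it only shrinks a real difference. Bias without a true effect needs a mechanism that differs by arm. In one such illustration (absence tied to the score in the treated arm only, g = 1), a true 0 becomes 1.6 to 2.5 points in favour of control. The documents give no reason to expect this, and section 5.0 blinds patients to their arm.

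**The size is small and assumed.** At g = 1 the loss of 0.94 points is 0.94/4.17 = 0.23 of one standard error, and two arms at two visits stand in for three arms at six. This stands: the figures show direction and order of size and do not forecast the result.

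**The model is not a full cure.** If current wellbeing drives absence, most of the loss remains. This also stands, and is why the model needs phone capture and a sensitivity analysis beside it.

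**The extra ten patients.** A reader might take the gap between the stated total of 85 and 3 × 25 = 75 as a dropout allowance. The documents never describe it so, and added numbers would not correct bias.

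**Conclusion.** The concern holds as a conditional one. The test named in section 6.0 is a weak choice for scores collected over a year, and the plan has no rule for missing scores. If local steroid works, and recovered patients respond less by any route, later differences are attenuated. The illustrated loss is about 12% (7.6 seen as 6.7) with no phone capture and about 4% (7.3) with half captured. It rests on the assumed correlation of 0.6, 25% missing and log-odds of 1 per SD. A stronger dependence roughly doubles the loss. With no true effect and a shared mechanism there is no bias. If absence is unrelated to scores, the plain test gives up only about 5% in standard error.

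The change is worth making because it is cheap and must be settled before outcome data are seen. The documents do not show that the trial's result would be reversed.

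**What to change.** **Section 6.0**

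- Replace the t-test or ANOVA for EAT-10, VHI-10 and EQ-5D with a mixed model for repeated measures containing arm, visit, arm-by-visit and the pre-operative score. Fit it by likelihood to every observed post-operative score from all randomised patients, and read the arm contrasts at each visit from it. Six visits need 6 × 7/2 = 21 unstructured covariance parameters, so name a simpler fallback structure in advance.
- Name the visit of main interest and the cut-off that defines dysphagia. Analyse incidence with the matching repeated-measures logistic model. Fit that by likelihood too, because ordinary estimating equations would not keep the benefit under score-related absence. State a fallback in case late events are too few for it to converge.
- Add a sensitivity analysis in which missing scores are allowed to be better than the model predicts, over a stated range and separately by arm.
- Score skipped items by each instrument's own rule, or prorate from the answered items when a stated minimum number is answered. Do not use a raw sum.

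**Section 5.0**

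- Make the phone questionnaire the default after a missed visit, including for patients who stop attending but still agree to contact. Record a telephone number for every subject.

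**Cost.** New plan wording, modest programming and some phone calls in a mode already permitted; no extra patients or visits. The main model assumes that absence is explained by recorded scores. The plain test needs a stronger assumption, and the sensitivity analysis shows how much the weaker one matters.

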3.0 SELECTION OF SUBJECTS

3.1 INCLUSION CRITERIA:

- All patients undergoing ACDF (single or multi-level) for the treatment of cervical radiculopathy or myelopathy with Drs. [name], [name], and [name].
- All subjects must have given signed, informed consent prior to registration on study.

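### Surgeon-graded, ordered dysphonia is left to a pooled unordered chi-square, and no analysis has a surgeon term: the tests stay valid, but precision can be gained cheaply

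*Combined protocol and SAP*

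**What the plan says.** The analysis in Section 6.0 reads "We will use T score or ANOVA to compare EAT-10 scores, VHI scores, and EQ-5D, and Chi square for subjective findings", followed by "The P value will be set at 0.05". No section mentions a surgeon or site term, a stratified test, or a test for ordered categories.

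Section 3.1 defines eligibility by operating surgeon: "All patients undergoing ACDF (single or multi-level) for the treatment of cervical radiculopathy or myelopathy with Drs", followed by three names (removed from the public copy). Under Section 4.0, "Each collaborating site will be involved in subject recruitment, consent, and all data collection". The synopsis lists four centres.

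In Section 5.0 the patients complete EAT-10 and Bazaz themselves, and VHI-10 is also a questionnaire. The surgeons separately listen to the patient's "voice at these different time points and comment on dysphonia as being absent, mild, moderate, or severe". No common calibration of the raters is described. Allocation is by one shuffled set of envelopes, with no strata by surgeon or site.

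Section 6.0 does not name the surgeon's voice grade or Bazaz. I take both to be among its subjective findings, and so assigned to chi-square.

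**The concern.** Two kinds of information that the trial will hold go unused.

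The first is the order of the grades. A chi-square of three arms by four grades spreads its power over (3 − 1) × (4 − 1) = 6 degrees of freedom and treats a move from severe to absent like any other change of category. A mean-score test uses 3 − 1 = 2. For two arms the figures are 3 and 1.

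The second is the surgeon. For the voice grade the surgeon is the rater, so pooling mixes the thresholds of three raters. For the questionnaire scores the surgeon performs the approach and plating, and any difference in technique or case mix stays in the error term. Because the envelopes are not stratified, the mix of surgeons can also differ between arms by chance.

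At 25 patients per arm, a modest gain in precision is worth having if it costs almost nothing.

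**Working it through.** **The plan's own figure.** Section 6.0 reports power of 0.92 from 25 per group and "estimated standard deviation of EAT-10 as 12.7", but states no difference, so the figure cannot be reproduced, only solved backwards. Assuming a two-sided 0.05 level:

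- SE = 12.7 × √(2/25) = 3.59.
- Difference = (1.96 + 1.405) × 3.59 ≈ 12.1 points, or 12.1/12.7 = 0.95 SD.
- An exact t-test gives 12.3 points. A three-group ANOVA gives 11.7 if one group differs and 13.5 if the means are evenly spaced.

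**Validity.** In simulations with three surgeons, unstratified allocation and 0 to 20% of variance between surgeons, type I error of the unadjusted ANOVA was 0.047 to 0.054.

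**Voice grade, planned test against proposed test.** Inputs: 25 per arm (Section 6.0), three surgeons (Section 3.1), four grades (Section 5.0). The cut-points between grades, the arm effect of 1.2 logits and the rater shifts are assumptions. The proposed test takes, within each surgeon, the sum of grade scores in each arm minus its expectation (patients in that arm × that surgeon's mean grade), adds these over surgeons, and refers the standardised result to chi-square.

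| Raters | Pooled chi-square | Surgeon-stratified mean-score test |
|---|---|---|
| Agree | 0.27 | 0.41 |
| Neighbours differ by 1.0 logit | 0.23 | 0.41 |

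Type I error stayed near 0.05.

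**Where that gain comes from.** A separate simulation, with its own assumed settings, compared mean-grade regression without and with a surgeon term:

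- raters agree: 0.461 without, 0.457 with;
- 0.5 logit between neighbours (a further run): 0.443 and 0.443;
- 1.0 logit: 0.39 and 0.43;
- 1.5 logits: 0.34 and 0.43.

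So when raters agree the gain comes from using the order. The surgeon term adds something only when raters differ by clearly more than 0.5 logit.

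**EAT-10 and other scores.** A surgeon factor with three levels multiplies the error variance by (1 − s), where s is the share of variance between surgeons. It costs two degrees of freedom and a little efficiency from chance imbalance. Simulated efficiency at s = 0 is about 0.97, so efficiency ≈ 0.97/(1 − s). Power is for one two-arm comparison, without → with the surgeon factor, at the implied 0.95 SD and at an assumed smaller effect of 0.7 SD (0.7 × 12.7 = 8.9 points).

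| s | 0.97/(1 − s) | Simulated efficiency | Power at 0.95 SD | Power at 0.7 SD |
|---|---|---|---|---|
| 0 | 0.97 | 0.97-0.98 | 0.906 → 0.901 | 0.68 → 0.67 |
| 3% | 1.00 | 1.00 | 0.913 → 0.915 | – |
| 5% | 1.02 | 1.01-1.03 | 0.915 → 0.926 | – |
| 10% | 1.08 | 1.08-1.10 | 0.916 → 0.939 | 0.68 → 0.71 |
| 20% | 1.21 | 1.22-1.23 | – | 0.68 → 0.76 |

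Results are similar with 45, 20 and 10 patients per surgeon. A closed-form check on the three-group ANOVA, starting from 0.92, gives 0.933 at 5%, 0.945 at 10% and 0.966 at 20%: gains of 1.3, 2.5 and 4.6 points.

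**The case against.** The strongest reply is that nothing in the documents shows that surgeons differ. Below about 3% of variance the surgeon factor gains nothing for EAT-10, and at the effect implied by the stated power the change over 0 to 10% is only about −0.5 to +2.5 points. This stands, and it is why the surgeon factor is the secondary part of the fix.

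Rater shifts of 1.0 to 1.5 logits between neighbours are also large: 2 to 3 logits between the extreme raters, an odds ratio of about e² = 7 to e³ = 20. This stands too, but the gain for the voice grade does not need such shifts, because most of it remains when raters agree.

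Other covariates have a claim. Preoperative EAT-10 is collected and the number of levels varies. True, but surgeon does not compete with them, and only surgeon identifies the rater.

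Finally, Section 6.0 is brief, and a chi-square need not mean an unordered pooled table. That is possible, but an analyst following the text would run exactly that, and nothing in it points to another test.

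**Conclusion.** The point holds as a cheap improvement in precision. It is firmest for the surgeon-graded dysphonia, where power rises from about 0.27 to 0.41 (raters agree) or from 0.23 to 0.41 (1.0 logit apart). These levels rest on assumed cut-points and a 1.2-logit effect. For EAT-10, VHI-10 and EQ-5D the balance runs from a loss of about 3% of efficiency to a gain of about 22% as the surgeon share goes from 0 to 20%; that share is an assumption.

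A reader might infer more than the documents support:

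- **The unadjusted tests are invalid, or their intervals too wide.** With a single unstratified shuffle they are valid. Intervals would be too wide only if allocation were balanced within surgeon, which is not described.
- **Omitting surgeon certainly costs power for EAT-10.** It does so only above about 3% of variance.
- **Rater differences contaminate the primary outcome.** Patients complete EAT-10 and Bazaz. An ordered test suits Bazaz because its grades are ordered, not because of the rater.
- **The stated 0.92 is overstated for this reason.** If 12.7 is a total SD, any such loss is already in it. If it is a within-surgeon SD, ANOVA power would be 0.906 at 5% and 0.889 at 10%. Section 6.0 does not say which.

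Whether the grading surgeon knows the arm is a separate question of bias, which stratifying by surgeon would not resolve.

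**What to change.** In Section 6.0:

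1. Analyse the surgeon-graded dysphonia with a Cochran-Mantel-Haenszel mean-score test stratified by surgeon, or an ordinal model with a surgeon term, in place of the pooled chi-square.
2. Use the same mean-score test for Bazaz, because its grades are ordered.
3. Prespecify operating surgeon as a fixed factor in the comparisons of EAT-10, VHI-10 and EQ-5D. If each surgeon works at one site, this also covers site; with names removed, I cannot confirm that.

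Add a surgeon code to the Data Collection Form, which has columns only for the subject number and four complications. The Coded Identifier Form has no such field either. Record the code before identifiable data are destroyed under Section 7.0.

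The cost is a sentence or two of text, one column on a form, two degrees of freedom, and up to about 3% of efficiency for the scores if surgeons do not differ. No extra visits or measurements are needed. The choice should be fixed before outcome data are seen, since a surgeon term added afterwards would be open to challenge.
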